10.2.7. Active Infections or Live Vaccines

Given the mechanism of action of etrasimod and the known pharmacodynamic effect of lymphocyte lowering, subjects with known active infections will be excluded from the study. Live vaccinations cannot be administered within 4 weeks of Screening, during Screening, during the Treatment Periods with study treatment, or 2 weeks after treatment completion.

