It is assumed that the percent change in EASI from Baseline to Week 12 will be normally distributed with an estimated standard deviation (SD) of 41%. Assuming a 1:1:1 randomization, 120 subjects (40 subjects each in 1 mg etrasimod, 2 mg etrasimod, and placebo groups) is sufficient to achieve at least 90% power to detect a difference of 35% in EASI from Baseline to Week 12 between each of the etrasimod treatment groups and placebo by a 2-sample t-test using a 1-sided significance level of 0.025. This sample size also accounts for an estimated drop-out rate up to 25%.

D. Treatment Randomization

Randomization will be stratified by vIGA score at Baseline (3 versus 4) and region

E. Assessment Schedule

For the statistical analysis, DB Treatment Period will include 12 weeks treatment and 4 weeks safety follow-up; OLE Period will include 52 weeks treatment and 4 weeks safety follow-up. The date at which the subject is randomized will be referred to as the “Baseline/Day 1”. Subjects will be requested to attend the following scheduled visits for the DB Treatment Period from their Baseline/Day 1 visit: Week 1, 2, 4, 6, 8, 12 and Week 16/SFU visit. For the OLE Period, Week 16 (this will be same as Week 16 in the DB Treatment Period), Week 17, 18, 20, 24, 28, 32, 40, 48, 56, 68, and Week 72/ SFU. The acceptable visit window for scheduled visits for the DB Treatment Period including Week 16, and Week 17 and 18 in OLE Period is ± 3 days, for all the other OLE visits, the scheduled visit window is ± 7 days. Visits that subjects make to the clinic outside the visit window are recorded as unscheduled visits.

Please refer to protocol for details.

5. General Analytical Considerations

A. Data Sources and General Rules

Data are recorded on electronic case report form (eCRF) for each subject screened/enrolled in this study. These forms will be used to transmit information collected during the study to the Sponsor and regulatory authorities, as applicable. Laboratory data, [REDACTED] blood samples and [REDACTED] data are collected separately by the selected vendors. Section 14 of the protocol provides additional details regarding data handling and record keeping.

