Modified Full Analysis Set (mFAS)	The mFAS consists of all randomized subjects who received at least 1 dose of study treatment, have a baseline measurement, and have at least 1 post-randomization measurement. The mFAS is endpoint specific, therefore subjects included in the analysis set for 1 endpoint may differ from another endpoint, based on the baseline and post-baseline data.
Per Protocol Set (PPS)	The PPS consists of all subjects in the FAS who adhere to the protocol. The PPS will be used in sensitivity analyses of the primary and key secondary endpoints to evaluate the influence of major protocol violators and protocol deviators on the primary results. Specific reasons for warranting exclusion from this analysis set will be documented prior to database lock and may include, but are not limited to: 
 • Not meeting critical inclusion/exclusion criteria • Study treatment noncompliance • Receiving incorrect study treatment • Missing more than a defined number of visits while still on study • Chronic prohibited medication use while on study treatment
Treatment Completer Set (TCS)	The TCS includes subjects in EASI or vIGA specific mFAS who have completed 12 weeks of study treatment in DB Treatment Period.
Safety Set (SAF)	The SAF includes all randomized subjects who received at least 1 dose of study treatment.
[REDACTED]	[REDACTED]
Post Hoc Analyses Set (PHAS)	The PHAS excludes 9 subjects from the Full Analyses Set in the 2 mg treatment group with unwarranted dose interruption due to lymphocyte decrease between week 4 and 12
OLE Period	
OLE Safety Set (OLE SAF)	The OLE SAF includes all subjects who enrolled in the OLE Period and received at least one dose of etrasimod. All safety

	
and efficacy analysis in the OLE Period will be performed over OLE SAF. For the analyses of efficacy endpoints, subjects will further be required to have at least one efficacy measurement in the OLE Period. Therefore, efficacy evaluable set is endpoint specific.

H. Missing Data

In order to analyze primary and secondary efficacy endpoints at Week 12 in the FAS, the handling of missing data and rescue medication uses are specified in Section 8.B - 8.C. No imputation will be implemented for exploratory efficacy and safety endpoints. The handling of missing reporting information for safety assessments are specified in Section 9.

I. Data Display Characteristics

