The scores from the 7 questions are added up to give an overall POEM score (0-28). An overall POEM score of 0-2 = ‘clear/almost clear’, 3-7 = ‘mild’, 8-16 = ‘moderate’, 17-24 = ‘severe’, and 25-28 = ‘very severe atopic eczema’.

- **DLQI** is a 10-item patient-reported outcome (PRO) measure that assesses the extent to which the skin condition has affected the subject’s quality of life over the past week, including 6 domains (daily activities, personal relationships, symptoms and feelings, leisure, work/school, and treatment). Total score (0-30) will be calculated as the sum of 10 questions with each ranging from 0 to 3. The scoring of each answer is as follows:

Very much	Scored 3
A lot	Scored 2
A little	Scored 1
Not at all	Scored 0
Not relevant	Scored 0
Question unanswered	Scored 0

Question 7	Question 7A	Score
Yes	Any response	3
No	A lot	2
No	A little	1
No	Not at all	0
Not relevant	Any response	0

[figure not shown]
If one question is left unanswered this is scored 0 and the scores are summed and expressed as usual out of a maximum of 30. If two or more questions are left unanswered the total DLQI score is missing. If question 7 is answered ‘yes’ or ‘not relevant’, then the answer of 7a will be ignored.

B. Primary Efficacy Outcome Analysis

The primary endpoint of percentage change in EASI from Baseline to Week 12 will be analyzed based on the FAS using an analysis of covariance (ANCOVA) model. The ANCOVA model will include treatment group as factors, Baseline EASI score and the two randomization factors of baseline vIGA (3 versus 4) and

region [REDACTED] as covariates. EASI scores after rescue medication use will be set to missing. All missing EASI scores at scheduled visits up to Week 12 will be imputed using a multiple imputation (MI) technique with a fully conditional specification (FCS) method and predictive mean matching (PMM) for EASI scores (Heitjan 1991, van Buuren 2007). The rescue medications considered for the purposes of efficacy analysis will include topical and systemic corticosteroids used during the DB Treatment Period of the study.

For MI, 100 imputation models will be generated, including treatment, baseline vIGA (3 versus 4), region [REDACTED] baseline EASI score, and EASI scores at the previous scheduled visits. Percent change in EASI at Week 12 will be derived from the imputed EASI values.

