Multiple results of ANCOVA (least square [LS] means and LS mean difference between etrasimod and placebo) for each MI dataset will be combined and reported along with 95% CI and p-value and using Rubin's method ([REDACTED]).

All subjects are required to have a baseline EASI score upon randomization. In the unlikely event that a subject is missing baseline EASI, the baseline value will be imputed first using the above covariates. The imputation model will be modified as appropriate based on the actual data.

In addition to the primary method for handling missing data and rescue medication use in the FAS, the following sensitivity analyses will be performed using alternative methods and/or in alternative analysis set:

- FAS, MI tipping point analysis

A tipping point analysis (Carpenter and Kenward 2013) will be performed to investigate the robustness of departures from the missing at random (MAR) assumption in the MI model by applying a specified sequence of shift parameters that modify the imputed EASI values, as follows:

- Missing EASI values will be imputed 100 times, following the MI method described above, with adjustment to the imputed EASI by shift

parameter $S_1=0.5$ in both etrasimod groups. A positive adjustment assumes a worsened outcome. The adjusted EASI value will be capped at 72. Imputed percent change in EASI will be derived accordingly. The MNAR statement with the ADJUST option in PROC MI will be used to apply the shift parameter.

- Each of the 100 completed datasets applying the shift parameters will be analyzed using an ANCOVA model as described above. The results from the 100 completed datasets will be combined for inference using PROC MIANALYZE.
- Repeat the above steps, with adjustment by shift parameter $S_2=1.0$ in both etrasimod groups. Repeat the process for the following pre-specified shift parameters: 0.5, 1.0, 1.5, 2.0...71.5, 72
- The shift parameters that result in a reversed study conclusion (i.e., p-value increases from <0.05 to ≥ 0.05) will be indicated.
- mFAS, using OC (observed data regardless of rescue medication uses and without imputation)

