A post hoc analyses set (PHAS) will be defined by excluding 9 subjects [REDACTED] from the full analysis set in the 2mg etrasimod group. The efficacy of treatment in these subjects were impacted by unwarranted dose interruption between week 4 and 8. The following analysis will be repeated using the post hoc analysis set:

- The primary outcome (percentage change in EASI from Baseline to Week 12) will be analyzed using the same ANCOVA and MMRM model described in [section 8 \(subsection B\)](#).
- EASI-75 and VIGA response rate (i.e. proportion of subjects achieving a validated Investigator's Global Assessment (vIGA) of 0 or 1 (on a 5-point scale) and a reduction from Baseline of ≥ 2 points) will be analyzed using the same CMH analysis described in [section 8 \(subsection C\)](#).
- Percentage in weekly peak NRS will be analyzed with the same MMRM model described in [section 8 \(subsection D\)](#).
- Weekly peak pruritus NRS with ≥ 3 and ≥ 4 reduction will also be analyzed with the same CMH analysis described in [section 8 \(subsection C\)](#).

B. Additional Exploratory Outcomes

The following additional outcomes will be explored:

- Proportion of subjects achieving an improvement (reduction) of ≥ 4 points in POEM from Baseline to Week 12.
- Proportion of subjects achieving an improvement (reduction) of ≥ 4 points in DLQI from Baseline to Week 12.
- Proportion of subjects achieving an improvement (increase) of ≥ 2 points in PGA from Baseline to Week 12.
- Proportion of subjects achieving an improvement (reduction) of ≥ 3 points in office based peak pruritus from Baseline through Week 12
- Proportion of subjects achieving an improvement (reduction) of ≥ 4 points in office based peak pruritus from Baseline through Week 12

The above outcomes will be analyzed in the FAS and the PHAS using the Cochran-Mantel-Haenszel method (CMH) adjusted for randomization stratification factors of baseline vIGA score (3 versus 4) and region [REDACTED]. Missing data will be imputed using the NRI method. The number, percentage of subjects achieving each outcome and Clopper-Pearson exact 95% confidence intervals will be reported. The differences in proportion between treatment groups, along with p-values and the 95% CIs will also be reported.

[figure not shown]

C. Sensitivity Analysis for Percent Change in EASI

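### The Post Hoc Analysis Set drops 9 subjects from the 2 mg arm alone for an on-treatment event, so its 2 mg comparisons are no longer randomised, yet they carry p-values

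*SAP*

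**What the plan says.** - **The set.** SAP 5.G, Table 2: "The PHAS excludes 9 subjects from the Full Analyses Set in the 2 mg treatment group with unwarranted dose interruption due to lymphocyte decrease". Table 2 places the interruption between weeks 4 and 12. The definition names no matching exclusion for 1 mg or placebo.
- **The reason.** SAP 12.A: "The efficacy of treatment in these subjects were impacted by unwarranted dose interruption between week 4 and 8". This window is shorter than the one in Table 2.
- **The link to the drug.** Protocol 10.2.7 explains its exclusion of active infections with the words "Given the mechanism of action of etrasimod and the known pharmacodynamic effect of lymphocyte lowering".
- **The use.** SAP 12.A repeats seven efficacy analyses in the PHAS by the Section 8 methods, which report p-values. SAP 12.B adds five responder outcomes by CMH in both the FAS and the PHAS, and states: "The differences in proportion between treatment groups, along with p-values and the 95% CIs will also be reported".
- **The labels.** SAP Section 1 says ad hoc output will be marked as such. SAP 5.F makes all double-blind pairwise comparisons exploratory, with no Type I error adjustment. SAP Section 6 plans baseline summaries for the FAS, SAF and PPS, but none for the PHAS or the 9 subjects.

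**The concern.** Randomisation makes the arms comparable at baseline. Removing subjects from one arm because of something that happened on treatment undoes this for every contrast with that arm. Here the trigger is also tied to what the drug does to lymphocytes. The per-protocol and completer sets also condition on post-randomisation events, but their stated criteria apply to every arm, whereas the PHAS definition names one.

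Section 12.A invites the reader to take the PHAS result as the 2 mg effect without the interruptions. Deletion does not isolate that effect. It mixes what the interruption cost the 9 subjects with how they would have differed from the other 2 mg subjects anyway. The post hoc label tells the reader that the analysis was unplanned; it does not say that the 2 mg comparison has lost its randomised basis. The visible text gives no operational definition of *unwarranted*, and the two windows disagree.

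**Working it through.** **Inputs.** 40 per arm, SD 41 points, difference 35 points, one-sided 0.025, dropout up to 25% (SAP 4.C); 9 subjects removed (SAP Table 2). The actual 2 mg arm size and the outcomes of the 9 are not given.

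**The plan's own figure.** A two-sample t-test with these inputs needs 30 evaluable per arm (power 90.2%), and 30/(1 − 0.25) = 40. The design reproduces. At 31 versus 40 without dropout, power at the planning difference is still 94.0%, so the problem is bias, not lost power.

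**Number of PHAS analyses.** 12.A: EASI percent change by ANCOVA and by MMRM (2), EASI-75 and vIGA response (2), weekly peak NRS percent change (1), NRS reductions of at least 3 and at least 4 (2), giving 7. 12.B: 5. Total 12.

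**Share removed.** 9/40 = 22.5%. For other arm sizes: 9/35 = 25.7%, 9/50 = 18.0%.

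**What deletion estimates.** Let R be the mean improvement of the retained 2 mg subjects, E the mean the 9 would have shown without interruption, and D the improvement they lost to it. Put S = R − E.

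- FAS mean = [(n − 9)R + 9(E − D)]/n
- PHAS mean = R
- Uninterrupted mean = [(n − 9)R + 9E]/n
- PHAS − FAS = (9/n)(S + D)
- Bias of the PHAS for the uninterrupted effect = (9/n)S

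At n = 40, one observed shift of 0.225 × 20 = 4.5 points fits all of these:

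| S | D | Bias |
|---|---|---|
| 20 | 0 | 4.5 |
| 10 | 10 | 2.25 |
| 0 | 20 | 0 |
| −10 | 30 | −2.25 |

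Comparing PHAS with FAS therefore cannot show how much of the change is bias. For S = 10 and 20 the bias is 2.57 and 5.14 points at n = 35, and 1.8 and 3.6 at n = 50.

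**Error rate with no true effect.** SE = 41 × √(1/31 + 1/40) = 9.81, with 69 df.

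- S = 10: noncentrality 2.25/9.81 = 0.229; two-sided rejection 5.59%, of which 4.15% favours 2 mg (nominal 2.5%).
- S = 20: 4.5/9.81 = 0.459; 7.38%, of which 6.58% favours 2 mg.

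Across n = 35 to 50 the two-sided rates are 5.5–5.7% and 7.0–7.6%.

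**What imputation would gain.** This was simulated with S = 20, 40 per arm, SD 41, no treatment or interruption effect, and a correlation of 0.5 or 0.7 between pre-interruption and Week 12 scores. The imputation used predictive mean matching with 30 imputations and Rubin's rules; there were 4,000 runs per scenario.

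| Share of the gap predicted by pre-interruption score | PHAS bias | Bias after set-to-missing and MI | MI two-sided rejection |
|---|---|---|---|
| all | 4.4–4.6 | 0.4–0.6 | 4.3–4.5% |
| half | 4.3–4.7 | 2.2–2.6 | 4.9–5.1% |
| none | 4.4–4.7 | 4.3–4.7 | 7.0–7.3% |

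The spread in PHAS bias is simulation noise around the exact 4.5. All figures are unadjusted for baseline covariates.

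**The case against.** **It is disclosed.** The set is called post hoc, sits under a post hoc heading, and states openly who is removed and why. No decision rule uses it, and the FAS analyses stand. All of this is true and limits the weight: the defect concerns how PHAS results are reported and read. It does not remove the defect, because none of the labels says that the 2 mg contrast is no longer randomised.

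**The error rates rest on assumed gaps, and the SAP controls no error rate.** Also true. At S = 0 there is no bias. If stronger lymphocyte decrease goes with better response, S is negative and deletion works against 2 mg. The structural point is certain; the numbers only illustrate it.

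**The exclusion may not be selective.** No subject on 1 mg or placebo is shown to have had such an interruption and been kept, and an interruption that was not called for may say little about prognosis. Both are possible, but the visible text allows neither to be checked. Redacted text may define *unwarranted*, so its absence carries little weight here.

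**The remedy is partial.** It replaces only some of the 12 analyses, is itself post hoc, and gains nothing where earlier scores do not predict the gap. The simulation also used a simpler imputation model than SAP 8.B, which has 100 imputations and more covariates. These points stand. They are why a tipping-point step is needed and why the other PHAS tables should become descriptive.

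**Conclusion.** The concern holds. The PHAS contrasts involving 2 mg are not randomised comparisons, and the SAP attaches p-values and confidence intervals to them in 12 analyses. At 40 per arm the set discards 22.5% of the 2 mg arm. Bias for the uninterrupted effect is 0.225 × S: 2.25 points at S = 10 and 4.5 at S = 20, with two-sided error of 5.6% and 7.4%. S, D, the correlations and n = 40 are assumptions, and neither the size nor the sign of the bias can be derived from the documents. The FAS results and the 1 mg versus placebo contrast keep all their randomised subjects. The change should be made, but the primary result does not depend on it.

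**What to change.** 1. Beside the unchanged FAS result, report an analysis of all randomised subjects with EASI set to missing from the start of a qualifying interruption. Write one operational definition from the recorded start date and reason, apply it without regard to arm, and give the number meeting it per arm; SAP 9.A already summarises dose interruptions.
2. Impute with the SAP 8.B model, which already includes treatment, "baseline EASI score, and EASI scores at the previous scheduled visits". SAP 4.E lists "scheduled visits for the DB Treatment Period from their Baseline/Day 1 visit: Week 1, 2, 4, 6, 8, 12 and Week 16/SFU visit", so Weeks 1, 2 and 4 are available at or before the earliest stated interruption. Derive EASI-75 as in 8.C. For weekly peak NRS percent change, use the 8.D MMRM in the FAS with post-interruption values set to missing.
3. Extend the 8.B tipping-point shifts to these imputed values ("A positive adjustment assumes a worsened outcome"). Show the estimate and interval over the range of shifts, since the 8.B rule flags only a p-value that crosses 0.05 and is silent if the starting result is not below it.
4. State that the analysis assumes missing at random given baseline and pre-interruption scores, that the imputed values draw largely on retained 2 mg subjects, and that it too is post hoc.
5. Present every remaining PHAS table (EASI MMRM, vIGA, NRS response, the 12.B outcomes) as descriptive, with a statement that the 2 mg comparison is not randomised. Preferably add baseline characteristics of the 9 beside the retained 2 mg subjects.
6. Reconcile the interruption window in Table 2 with that in 12.A.

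**Cost.** SAP wording, one definition, one set-to-missing rule in code already specified, and optionally one baseline table. No new data are needed. The definition may be met rarely or never on placebo.

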10.3.5. Patient-Reported Outcomes

10.3.5.1. Pruritus Numeric Rating Scale

The pruritus NRS is a simple assessment tool that subjects will use to report the intensity of their pruritus (itch). The scale for the pruritus NRS is from 0 to 10 with 0 being “no itch” and 10 being “the worst itch imaginable.”

At Baseline and subsequent visits, subjects will be asked to rate the intensity of their itch (maximum/peak and average) over the previous 7 days. Subjects will also be asked to rate their average itch intensity over the previous 24 hours and their maximum itch intensity in a daily diary ([Stander 2013](#), [PruritusResources 2019](#)).

The pruritus NRS will be assessed at time points according to the [REDACTED].

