This plan will cover the analyses for: 1) the primary database lock after the completion of the Double-Blind (DB) Treatment Period; 2) the final database lock after the completion of the Open-Label Extension (OLE) Period. The plan will be finalized before the time of primary database lock and treatment unblinding. After that, the SAP may be amended to accommodate ad hoc analyses before the final database lock. Ad hoc analyses will be labeled as such on the output and identified in the Clinical Study Report.

2. Protocol Objectives

A. Primary Objective

To assess the efficacy of etrasimod monotherapy (1 or 2 mg) in subjects with moderate to severe atopic dermatitis (AD) during the DB Treatment Period.

B. Safety Objective

To assess the safety and tolerability of etrasimod monotherapy (1 or 2 mg) in subjects with moderate to severe AD during the DB Treatment Period.

C. Open Label Extension Objective

To assess the long-term safety, tolerability, and efficacy of etrasimod monotherapy (2 mg) in subjects with moderate to severe AD.

3. Study Endpoints

A. Primary Efficacy Endpoint

Percent change in Eczema Area and Severity Index (EASI) from Baseline to Week 12.

[REDACTED]

B. Key Secondary Efficacy Endpoints

- Proportion of subjects achieving EASI-75, defined as a 75% reduction of EASI from Baseline to Week 12.
- Proportion of subjects achieving a validated Investigator’s Global Assessment (vIGA) of 0 or 1 (on a 5-point scale) and a reduction from Baseline of ≥ 2 points at Week 12.

C. Secondary Efficacy Endpoints

- Percent change in weekly peak pruritus numeric rating scale (NRS) from an itch daily diary from Baseline to Week 12.
- Proportion of subjects with improvement (reduction) in weekly peak pruritus NRS ≥ 3 from an itch daily diary from Baseline to Week 12.
- Proportion of subjects achieving EASI-50, defined as a $\geq 50\%$ reduction of EASI from Baseline to Week 12.
- Proportion of subjects achieving EASI-90, defined as a $\geq 90\%$ reduction of EASI from Baseline to Week 12.
- Change and percentage change in percent body surface area (BSA) AD involvement total and for each body region from Baseline to Week 12.

D. Exploratory Efficacy Endpoints

- Change in Dermatology Life Quality Index (DLQI) from Baseline to Week 12.
- Change in Patient Oriented Eczema Measure (POEM) from Baseline to Week 12.
- Percent change in SCORing Atopic Dermatitis (SCORAD), total and by symptom (severity, and subjective symptoms), from Baseline to Week 12.

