Statistical analysis will be performed following IQVIA Biotech standard operating procedures and on the IQVIA Biotech computer network. All statistical analysis will be performed using SAS Version 9.4 with program code prepared specifically for the project by qualified IQVIA Biotech statisticians and SAS programmers.

All observed and derived variables (e.g., change from baseline, percentage change from baseline, and response status) that are analyzed or summarized will be listed by subject. Descriptive statistics will provide an overview of the efficacy and safety results. For categorical parameters, the number and percentage of subjects in each category will be presented. For continuous parameters, descriptive statistics will include number of subjects, mean, SD median, minimum, and maximum.

B. Definition of Baseline and Study Day

Study day will be defined separately for the DB Treatment Period and OLE Period. For all subjects, Day 1 is the date of first study drug administration in the DB Treatment Period. This will be referred to as the **Overall Day 1**. For those enrolling into the OLE Period, an **OLE Day 1** will be additionally defined as the date of the first study drug administration in the OLE Period at Week 16.

Study day will be calculated relative to the date of Overall Day 1.

Similarly, Baseline will be defined separately for DB Treatment Period and OLE Period as follows:

[figure not shown]
- **DB Treatment Period:** baseline will be defined as the last available measurement prior to the first dose of the study drug in DB Treatment Period. Specifically, for vital signs (resting heart rate (HR), blood pressure (BP), body temperature, and respiratory rate) and [REDACTED], the Day 1 pre-randomization assessments will be used as baseline measurements. The lowest pre-dose HR measurement will be used for comparison to the post-dose HR measurement. This will be referred to as the **DB baseline**.

[figure not shown]
- OLE Period: for those enrolling into the OLE Period, an **OLE baseline** will be additionally defined as the last pre-dose measurement at Week 16 at Week 16.

Change from baseline is defined for both DB Treatment Period and OLE Period as the post-baseline value minus the baseline value unless otherwise specified. Percent change from baseline is calculated as follows: Percent change = (Change from baseline / Baseline) x 100.

C. Analysis Visit Window

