- **Pruritus NRS** is a simple assessment tool of the intensity of pruritus (itch) from 0 to 10 with 0 being “no itch” and 10 being “the worst itch imaginable.” Both maximum/peak and average NRS scores will be assessed.

In a daily diary, subjects are asked to rate their worst itch and itch on average over the previous 24 hours. The weekly average NRS (peak and average) will be analyzed as efficacy endpoints, and derived as per the following schedule and rule:

- For DB Treatment Period: Baseline (Day 1), Week 1 (Day 2 to 8), Week 2 (Day 9 to 15), Week 3 (Day 16 to 22)...Week 12 (Day 79 to 85)... and Week 16 (Day 107 to Day 113 or Day of Week 16 visit whichever comes first for subjects enrolled into OLE Period).
- For OLE Period: Week 17 (Day of week 16 visit +1 to Day 120), Week 18 (Day 121 to 127), Week 19 (Day 128 to 134)...Week 28 (Day 191 +).
- Subjects must complete at least 3 NRS entries to calculate the weekly average. The weekly average will be considered missing if more than 4 entries are missing for that weekly interval. The baseline for the analysis of diary data is Day 1.

At each scheduled office visit, the subject is asked to rate their worst itch and itch on average in the past 7 days and these are recorded as office based peak and average NRS.

- **BSA AD** will be assessed for each region of the body and combined. The region percent affected BSA is the affected percentage (0-100) at each body region. The total percent affected BSA is the sum of multiplying region percent affected BSA by the multiplication factor with a maximum of 100.

Body Region	Multiplication Factor
Head and Neck	9%
Upper Limbs (right)	9%
Upper Limbs (left)	9%
Lower Limbs (right)	18%
Lower Limbs (left)	18%
Anterior Trunk	18%
Back	18%
Genitals	1%

- **PGA** includes 2 questions **for wellness and appearance**. Subjects will rate their overall well-being based on a 5-point Likert scale from poor to excellent. Response choices are: ‘Poor’, ‘Fair’, ‘Good’, ‘Very Good,’ or ‘Excellent’.

- **POEM** consists of 7 questions asking patients to rank how many days over the past 7 days they have experienced specific AD-related symptoms. Each of the seven questions carries equal weight and is scored from 0 to 4 as follows:

No days	Scored 0
1-2 days	Scored 1
3-4 days	Scored 2
5-6 days	Scored 3
Every day	Scored 4

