- Longitudinal continuous variables (percent change in weekly peak pruritus NRS, change and percentage change in %BSA) measured at visits (weeks) up to Week 12 will be analyzed with a MMRM model based on FAS using observed data. The MMRM model will include treatment group, visit (week), and interaction of treatment-by-visit (week) as factors, and baseline measure and randomization stratification factors as covariates. An unstructured covariance matrix will be specified for the MMRM model. If the model does not converge using an unstructured covariance matrix, an auto-regressive AR(1) structure will be tested. If AR(1) fails to converge, a compound symmetric structure will be used. LS means at visit (week) and LS mean differences at visit (week) between treatment group with p-values and corresponding 95% CIs will be reported.
- Dichotomous measures (weekly peak NRS ≥ 3 reduction, EASI-50, and EASI-90) at Week 12 will be analyzed in the same way as for the key secondary endpoints based on FAS with CMH method adjusted for randomization stratification factors of baseline vIGA score (3 versus 4) and region [REDACTED]. Missing data (including those after use of rescue medication) will be handled by NRI method. The number, percentage of subjects achieving the goal and Clopper-Pearson exact 95% confidence intervals will be reported. The differences in proportion between treatment groups, along with p-values and the 95% CIs will also be reported. Weekly peak NRS ≥ 3 reduction will be assessed among the subset of subjects whose baseline peak NRS is ≥ 3 .

Sensitivity analyses will be performed in the PPS and TCS using observed data.

E. Exploratory Efficacy Outcome Analysis

Below exploratory endpoints will be analyzed in a similar manner as the secondary continuous variables with the MMRM model based on FAS using observed data.

- Change in DLQI from Baseline to Week 12.
- Change in POEM from Baseline to Week 12.
- Percent change in SCORAD total and individual symptom scores from Baseline to Week 12.

The primary and sensitivity analysis for all efficacy endpoints are summarized in **Table 3**.

Table 3 Summary of Efficacy Analyses

Efficacy Endpoint	Primary Analysis	Sensitivity Analysis
DB Treatment Period		
Primary		

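### The diary itch baseline is a single Day 1 entry set against weekly means, which costs precision on the itch secondary endpoints by an amount the documents cannot fix

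*SAP*

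**What the plan says.** SAP 8.A (Pruritus NRS) gives the diary windows as "Baseline (Day 1), Week 1 (Day 2 to 8), Week 2 (Day 9 to 15" and so on in 7-day blocks to Week 12 (Day 79 to 85). For the quantity analysed it says "The weekly average NRS (peak and average) will be analyzed as efficacy endpoints", with the completeness rule "Subjects must complete at least 3 NRS entries to calculate the weekly average". It then fixes the reference value: "The baseline for the analysis of diary data is Day 1".

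That reference value is used in three places:

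- **Percent change.** SAP 3.C lists "Percent change in weekly peak pruritus numeric rating scale (NRS) from an itch daily diary from Baseline to Week 12" at the head of the secondary endpoints, and SAP 5.B defines "Percent change = (Change from baseline / Baseline) x 100".
- **The ≥3-point reduction** in weekly peak NRS (SAP 3.C and 8.D). SAP 12.A uses it again at ≥3 and ≥4 points in the post hoc set.
- **The responder denominator.** Under SAP 8.D this endpoint "will be assessed among the subset of subjects whose baseline peak NRS is" at least 3.

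The percent change is analysed by MMRM on observed data with the baseline measure as a covariate (SAP 8.D). The itch sensitivity analyses (SAP 8.D and Table 3) change the analysis set and use observed data, but none changes the baseline. Separately, Protocol 10.3.5.1 says that at Baseline and later visits "subjects will be asked to rate the intensity of their itch (maximum/peak and average) over the previous 7 days".

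**The concern.** The two ends of the change score are measured with different precision: one diary entry before treatment, a mean of 3 to 7 entries afterwards. A one-day baseline could not meet the SAP's own three-entry rule.

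Error in a denominator matters more than error in a covariate. Take a subject whose usual peak itch is 6 and whose Week 12 mean is 4, a true change of −33%. If Day 1 happens to read 4, the recorded change is 0%. If it reads 8, the recorded change is −50% and the 2-point fall becomes a 4-point response. A low Day 1 score can also keep a subject with substantial usual itch out of the responder subset.

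At stake are wider intervals for the itch estimates and some misclassified responders. The primary endpoint (EASI) and the key secondaries (EASI-75, vIGA) do not use this baseline.

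**Working it through.** **1. The plan's own figure.** Only EASI is powered (Protocol 11.2, SAP 4.C): difference 35, SD 41, one-sided 0.025, 40 per arm, dropout up to 25%.

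- Evaluable: 40 × 0.75 = 30 per arm, df = 58.
- Noncentrality: (35/41) × √(30/2) = 0.854 × 3.873 = 3.31.
- t-test power: 90.2%. The stated 90% reproduces.

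This gives 30 per arm for the itch check. Neither document states an itch SD, a day-to-day variance or an itch power, so every itch input below is an assumption.

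**2. How much noise a weekly mean removes.** With day-to-day SD s and lag-one autocorrelation ρ, one entry has noise variance s². A 7-day mean has (s²/7) × [1 + 2 Σ(1 − k/7)ρᵏ], k = 1 to 6.

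| ρ | bracket | share of s² that remains |
|---|---|---|
| 0 | 1 | 0.14 |
| 0.5 | 2.43 | 0.35 |
| 0.8 | 4.48 | 0.64 |

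For between-subject SD 1.8 and s = 1.5, the reliability of one entry is 3.24/(3.24 + 2.25) = 0.59. For a 7-day mean of independent days it is 3.24/(3.24 + 2.25/7) = 0.91. Averaging helps less as days become more alike.

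**3. Effect on percent-change power.** Simulated two-arm trials: 30 per arm, integer scores 0 to 10, mean 7, between-subject SD 1.8, placebo improvement 20%, extra drug effect 22 points, Week 12 residual SD about 1.8 to 1.9, ANCOVA on baseline at two-sided 0.05. Gain in power from a 7-day-mean baseline over Day 1, in percentage points:

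| ρ | s = 1.0 | s = 1.5 | s = 2.0 |
|---|---|---|---|
| 0 | 6 | 13 | 19 |
| 0.5 | 5 | 8 | 13 |
| 0.8 | 1 to 2 | 1 to 2 | 1 to 2 |

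For ρ = 0 the levels are about 68/59/49% with Day 1 and 75/71/68% with the 7-day mean. Separate runs differ by a point or two through simulation error.

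A second grid (mean 7.3, between-subject SD 1.5 to 2.0, s 0.5 to 1.5, ρ 0 to 0.8; 18 scenarios) gave the same direction throughout. The gain was 0.6 to 12.8 points for percent change and 0.8 to 13.4 for the ≥3-point endpoint.

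**4. Responder status.** In simulations with the step 3 inputs, 12 to 20% of subjects changed responder status between the two baselines. In the second grid's inputs with between-subject SD 1.5, s = 1.5 and ρ = 0, responder rates were 51.4% against 25.6% (difference 25.8 points) with Day 1, and 50.2% against 20.9% (difference 29.3 points) with the 7-day mean. The noise dilutes the contrast; it does not create one.

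**5. Does the office 7-day NRS solve it?** Absolute change adjusted for Day 1 alone gives 80/76/72% power (s = 1.0/1.5/2.0, independent days). Adding the office value, with an assumed recall-error SD of 1, gives 81/77/74%, a gain of 1/1/2 points, and about zero with autocorrelation. Against percent change with Day 1, leaving the percent scale alone gains 80 − 68 = 12, 76 − 59 = 17 and 72 − 49 = 23 points. On the absolute scale even a full 7-day diary baseline adds only 0.5 to 4.2 points (second grid).

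**Simplifications.** One Week 12 time point replaces the MMRM, and an unstratified test replaces CMH.

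**The case against.** The strongest reply is that the loss may be negligible. Nothing in the documents says how variable daily itch is. The largest gain, 19 points, needs independent days and a day-to-day SD (2.0) above the between-subject SD (1.8). At autocorrelation 0.8 the gain is 1 to 2 points. This stands: the direction is secure and the size is not.

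Other replies stand in part:

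- **The MMRM adjusts for baseline.** It does, and the simulated ANCOVA did too. Adjustment recovers part of the loss but leaves the noise in the denominator and in the 3-point cut-off.
- **All comparisons are exploratory** (Protocol 11.6, SAP 5.F). True, but estimates, intervals and p-values are still reported.
- **A like-for-like itch analysis exists.** SAP 12.B analyses ≥3 and ≥4-point reductions in office peak itch, with 7-day recall at both ends. It is post hoc, uses another instrument and does not cover percent change.

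A reader might infer more than the documents support:

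- *Bias in favour of one arm.* The rule applies equally to all arms.
- *A better baseline is already in hand.* The office item is a recalled worst score over a week, not a mean of daily peaks, and it adds little (step 5). Used to gate the diary responder subset, it would admit a subject with office 6 and Day 1 of 2, who cannot fall 3 points.
- *A missed Day 1 entry removes the subject.* The visible text has no diary-specific rule for this. SAP 5.B's general rule, the last measurement before first dose, could supply an earlier entry if one exists.
- *Pre-Day 1 diary entries exist, or do not.* The assessment schedule is redacted.

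**Conclusion.** The point holds as a loss of precision that follows from a stated rule. A one-entry baseline is compared with weekly means and serves as denominator, anchor and gate for the diary itch endpoints. Under the step 3 assumptions the cost in percent-change power is about 6 to 19 points with independent days, 5 to 13 at autocorrelation 0.5 and 1 to 2 at 0.8. Some responders are also misclassified. No single figure can be defended without itch variance data. The affected percent change is first-listed among the secondary endpoints but ranks below the two key secondaries, and the conclusions on EASI and vIGA are untouched.

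**What to change.** **If diary entries before Day 1 were collected:** in SAP 8.A, define the diary baseline as the mean of pre-dose entries in the 7 days up to and including Day 1, with at least 3 entries. Use it for the percent change, the ≥3-point reduction and the baseline ≥3 subset alike. Keep the Day 1 version as a sensitivity analysis.

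**If they were not:** keep the percent-change analysis, which is the protocol's endpoint. Add a supplementary MMRM of absolute change in weekly peak NRS adjusted for the Day 1 entry. The office 7-day peak NRS may be added as a covariate, with about 0 to 2 points of power expected from it. It should not gate the diary responder subset.

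**Timing.** SAP 12 already names post hoc sets and subgroups by treatment arm, so this version may follow unblinding. In that case add either version as a labelled ad hoc analysis, as SAP Section 1 allows, and leave the prespecified Day 1 analysis in place.

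**Cost.** A few lines of SAP text and one more analysis, with no new data. In the fallback case itch may be reported on two scales, and the text should say which one is the prespecified endpoint.
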